15.2.10 TEAEs leading to death

The incidence of all TEAEs leading to death will be presented by SOC and PT. A data listing of all TEAEs for death participants will be presented.

16. Safety laboratory tests

The following analysis will be applicable to both, part-1, and part-2 of the study.

16.1 Variables and derivations

All the reported lab parameters will be presented for the below categories as per protocol:

- Biochemistry
- Hematology
- Thick blood smear – Malaria
- Urinalysis
- Urine for drugs of abuse
- Pregnancy test
- FSH
- Coagulation
- Serology
- Alcohol breath test

Quantitative laboratory measurements reported as “< X”, i.e., below the limit of quantitation, or “> X”, i.e., above the upper limit of quantification, will be converted to X for quantitative summaries but will be presented as recorded, i.e., as “< X” or “> X” in the data listings.

16.2 Analysis

Population: Table: SAF

Listing: ENRL

Stratification: Table: By part and group

Listing: By part, group, participant, timepoint & parameter

Statistics: Summaries of all the laboratory tests will include descriptive statistics at each assessment of the following:

- Actual and change from baseline (number of participants, mean, SD, median, minimum & maximum) (for quantitative measurements) for which baseline data is collected. i.e., Biochemistry, Hematology.
- Frequencies and percentages (n and %) (for qualitative measurements). i.e., Thick blood smear – Malaria, Pregnancy test, Urinalysis, Urine for drugs of abuse, Alcohol breath test.)

Qualitative laboratory measurements will be compared with the relevant laboratory reference ranges and summarized as:

- Normal: Within the laboratory reference range (upper and lower limit included)
- Abnormal NCS: Abnormal not clinically significant
- Abnormal CS: Abnormal clinically significant
- High: Higher than the upper limit of the reference range
- Low: Lower than the lower limit of the reference range

Above categorizations and abnormal laboratory data will be flagged and presented in data listings.

The qualitative urinalysis data will be listed only. Those above lab parameters that will only be done in screening will be listed only.

17. 12-Lead ECG & Vital signs

The following analysis will be applicable to both, part-1, and part-2 of the study.

17.1 Variables and derivations

For ECG and vital signs, a baseline is defined as the last observation made before the first administration of study treatment.

The following vital signs parameters will be reported for this study:

- Blood pressure (Systolic and Diastolic)
- Heart rate
- Axillary temperature
- respiratory rate

All recorded in supine position.

The following 12-lead ECG parameters will be reported for this study:

- PR
- QRS
- QT
- QTcB
- QTcF
- HR

17.2 Analysis

Population: Table: SAF

Listing: ENRL

Stratification: Table: By part and group

Listing: By part, group, participant, timepoint & parameter

Statistics: Summaries of all 12-Lead ECG & vital parameters will include descriptive statistics at each assessment of the following:

- Actual and change from baseline (number of patients, mean, SD, median, minimum & maximum) (for quantitative measurements)
- Frequencies and percentages (n and %) (for qualitative measurements)

"Any Clinically Significant Abnormality Found in Vital Signs" will be found as "Yes" on the eCRF page of Vital signs, it will be summarized as Frequencies and percentages (n and%).

In ECG analysis, if triplicate ECG performed then the average of three repetitions will be calculated and used for the further evaluation.

The qualitative measurements of ECG will be categorised as (Normal, Abnormal Clinically Significant and Abnormal Not Clinically Significant) Above categorizations and abnormal data will be flagged and presented in data listings.

Additionally, QTcF data will be summarized using frequencies & percentages (n and %) as follows:

Absolute QTcF interval prolongation

- QTcF interval > 450 ms
- QTcF interval > 480 ms
- QTcF interval > 500 ms

Change from baseline in QTcF interval

- QTcF interval increases from baseline > 30 ms
- QTcF interval increases from baseline > 60 ms

The mean value of change from baseline QTcF parameters will be plotted by group and time point.

18. Primary Endpoint Analysis

18.1 To determine the relative bioavailability of a single oral dose of PQP dispersible granule formulation (Test) as compared to PQP hard tablet formulation (Reference) in the fasted state.

18.1.1 Variables and derivations

- AUC_{0-72h} : Area under the plasma concentration curve from time zero to 72 hours
- AUC_{0-168h} : Area under the plasma concentration curve from time zero to 168 hours
- AUC_{0-t} : Area under the plasma concentration curve from time zero up to the last quantifiable concentration
- $AUC_{0-\infty}$: Area under the plasma concentration-time curve from time 0 extrapolated to infinite time.
- C_{max} : Maximal plasma concentration

Comparisons of interest are as follows:

- Group 1: PQP hard tablet with Group 2: PQP dispersible granule

18.1.2 Analysis

Population: Table: PK

Listing: PK

Stratification: Table: By part and group

Listing: By group, participant, timepoint & parameter

Statistics: The relative bioavailability will be assessed for PQP using the ratio of the geometric means for $AUC_{(0-72h)}$, $AUC_{(0-168h)}$, $AUC_{(0-t)}$, $AUC_{(0-\infty)}$, and C_{max} as follows:

- For Part 1 the comparisons will be Group 2 PQP dispersible granule (320 mg, fasted) [test] over the Group 1 PQP hard tablet (320 mg, fasted) [reference].

To determine bioequivalence between PQP dispersible granule (320 mg) [test] and the PQP hard tablet (320 mg), In-transformed PK parameters AUC_{0-72h} , AUC_{0-168h} , AUC_{0-t} , $AUC_{0-\infty}$, and C_{max} will be analyzed using Type III sum of squares, with the fixed effect of treatment using General Linear Model (PROC GLM) in SAS software.

Each analysis of variance will include calculation of least square means (LSM). Two 1-sided tests procedure at 5% level of significance will be

used to compare the geometric LSM values of PK parameters determined after administration of test and reference products.

Point estimates of the ratio of geometric least squares means and its 90% CI of PQP dispersible granule (320 mg) and PQP hard tablet (320 mg) will be calculated and reported for ln-transformed PK parameters.

Total subject variability for the PQP dispersible granule (320 mg) [test] and PQP hard tablet (320 mg) PK data will be calculated and reported.

Summary statistics (i.e., mean, median, SD, CV%, minimum, maximum, n, geometric mean, geometric SD, and geometric CV%) will be calculated for blood concentrations for each time point and group. The same will be done for the PK parameters which will be listed for each individual and summarized by group.

19. Secondary Endpoints

19.1 To assess the effect of different types of meal composition on the PK of single doses of PQP dispersible granule formulation in healthy adult participants.

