### **5.2.1 Inclusion criteria**

Participants must fulfil all of the following criteria to be eligible for enrolment in this trial:

1. Female or Male aged  $\geq 18$  years to  $\leq 55$  years at the date of signing informed consent.
2. Ability to provide written, personally signed, and dated informed consent to participate in the trial, in accordance with the ICH Good Clinical Practice (GCP) and applicable regulations, before any trial-related procedures.
3. An understanding, ability, and willingness to fully comply with trial procedures and restrictions.
4. Female participants must agree to follow contraceptive requirements as indicated in Section 13.2.2, from at least 30 days prior to first dosage to 16 weeks after last dosage.
5. Agrees not to donate sperm or ova from the time of the first administration of trial medication until twelve weeks after the end of the systemic exposure of the trial drug.
6. Participants must have a body weight of 50 kg or greater and a BMI between  $18.0 \text{ kg/m}^2$  -  $30.0 \text{ kg/m}^2$  (inclusive) at screening.
7. Satisfactory medical assessment with no clinically significant or relevant abnormalities as determined by; medical history, physical examination, vital signs, 12-lead ECG and clinical laboratory evaluation that is reasonably likely to interfere with the participant's participation in or ability to complete the trial as assessed by the Investigator.

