#### 7.1.3 Physical Examination

A complete physical examination will assess general appearance including height and weight (at screening) and weight repeated (at Day-1) and the following body system: skin, lymph nodes, head, eyes, ears, nose, throat, respiratory, cardiovascular, abdomen, extremities, musculoskeletal, and neurological.

A targeted symptom directed physical examination will be assessed at any study visits as deemed necessary by the Investigator based on history of presenting complaint or clinical observations.

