4.2 Randomization

Healthy adult participants (male and female) will be randomly allocated to one of the 5 following treatment groups, dosing will be carried out in the fasted or fed state:

- During the study part 1, participants for fasted conditions will be randomly allocated to either group 1 (n=12) or group 2 (n=12), in order to assess the relative bioavailability of the dispersible granules formulation as compared to the hard tablet formulation.
 - Randomization will occur in blocks of 2 (each block contains 1 assignment from each of the groups 1 and 2).
- During study part 2, participants for fed conditions will be randomly allocated to either group 3 (n=12), 4 (n=12), or 5 (n=12), in order to assess the food effect after dosing of PQP dispersible granules formulation.

- Randomization will occur in blocks of 3 (each block contains 1 assignment from each of the groups 3, 4, and 5).

A computer-generated randomization schedule will be used and will be accessible only to the site-delegated study staff who will prepare the treatment for each participant according to the randomization allocation.

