11.2 Analysis

Population: Table: SAF and PK

Listing: ENRL

Stratification: Table: By part and group

Listing: By part, group and participant

Statistics: Baseline and Demographic variables will be summarized for each stratification factor and overall, also listed by participant number. The summaries will include descriptive statistics for continuous measures (number of participants, number of missing values, mean, SD, median, minimum & maximum) and for categorical measures (frequency, percentages, and number of missing values).

12. Exposure to IMP**12.1 Analysis**

Population: SAF

Stratification: Table: By part and group

Listing: By group and participant

Statistics: Planned dose and actual dose will be summarized descriptively (number of participants, number of missing values, mean, SD, median, minimum & maximum). Study drug administration information will be listed by participant number.

13. Medical history summary

The following analysis will be applicable to both, part-1, and part-2 of the study.

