19.1.2 Analysis

Population: Table: PK

Listing: PK

Stratification: Table: By part and group

Listing: By part, group, participant, timepoint & parameter

Statistics: The relative bioavailability will be assessed for PQP using the ratio of the geometric means for $AUC_{(0-72)}$, $AUC_{(0-168)}$, $AUC_{(0-t)}$, $AUC_{(0-\infty)}$, and C_{max} as follows:

For Part 2 the comparisons will be as follow.

- Group 3: High-fat meal (Fed) [test] over the Group 2 PQP dispersible granule (fasting) [reference]
- Group 4: Low-fat meal representative of African diet (Fed) [test] over the Group 2 PQP dispersible granule (fasting) [reference]
- Group 5: Whole milk 250 ml (Fed) [test] over the Group 2 PQP dispersible granule (fasting) [reference]

To determine bioequivalence between PQP dispersible granule (320 mg) [test] and each of different type of meal, ln-transformed PK parameters ($AUC_{(0-72h)}$, $AUC_{(0-168)}$, $AUC_{(0-t)}$, $AUC_{(0-\infty)}$, and C_{max}) will be

analyzed using Type III sum of squares, with the fixed effect of Treatment using General Linear Model (PROC GLM) of SAS software.

Each analysis of variance will include calculation of least square mean (LSM). Two 1-sided tests procedure at 5% level of significance will be used to compare the geometric LSM values of PK parameters determined after administration of test (different type of meal) and reference products.

Point estimates of the ratio of geometric least squares means of dispersible granules formulation between fed [high-fat meal, low-fat African meal, and milk] will be calculated and reported for In-transformed PK parameters.

Total subject variability for the dispersible granules formulation between fed [high-fat meal, low-fat African meal, and milk] PK data will be calculated and reported.

Summary statistics (i.e., mean, median, SD, CV%, minimum, maximum, n, geometric mean, geometric SD, and geometric CV%) will be calculated for blood concentrations for each time point and group. The same will be done for the PK parameters which will be listed for each individual and summarized by group.

19.2 To further evaluate the PK of a single oral dose of PQP granule formulation in the fasted state and different fed states in healthy adult participants.**19.2.1 Variables and derivations**

The following pharmacokinetic parameters will be calculated for piperaquine:

- C_{\max} : Maximal plasma concentration
- T_{\max} : Time at which the maximum plasma concentration occurs

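### The food-effect ratios compare Groups 3–5 with a non-randomised Part 1 reference and take no account of body weight, so any weight difference between the parts would enter as bias

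*SAP*

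**What the plan says.** The primary analysis in SAP 18.1.2 models the ln-transformed AUCs and Cmax "with the fixed effect of treatment using General Linear Model (PROC GLM) in SAS software". The food-effect analysis in SAP 19.1.2 models the same metrics "with the fixed effect of Treatment using General Linear Model (PROC GLM) of SAS software", with each fed group as test and fasted Group 2 as reference. Neither section names a covariate or a sensitivity model.

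On randomisation, SAP 4.2 says for Part 1 that "Randomization will occur in blocks of 2", one assignment each to Groups 1 and 2. For Part 2 it says "Randomization will occur in blocks of 3 (each block contains 1 assignment from each of the groups 3, 4, and 5". Group 2 is not in the Part 2 scheme, and no stratification factor is named. Protocol 1.6 (Study Design) makes the two parts sequential.

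Body weight is available for everyone. Protocol 7.1.3 records "height and weight (at screening) and weight repeated (at Day-1". Entry is limited only by Protocol 5.2.1: "Participants must have a body weight of 50 kg or greater and a BMI between" 18.0 and 30.0 kg/m². The planned dose of 320 mg is the same for all participants and is not scaled to weight. The SAP uses weight only descriptively. Section 11.2 says "Baseline and Demographic variables will be summarized for each stratification factor and overall", by part and group, for the safety and PK sets.

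**The concern.** In a parallel-group comparison of 12 versus 12, all between-participant variability falls into the contrast. If exposure after a fixed dose depends on body size, a difference in mean weight between the compared groups moves the geometric mean ratio.

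For Groups 1 and 2 such a difference can only be chance, and the confidence interval already allows for it. For Groups 3–5 against Group 2 nothing in the design balances weight. Recruitment is rolling (Protocol 5.2), the parts run at different times, and Protocol 1.6 promises only efforts towards gender balance. A difference between the parts would therefore be bias, which a treatment-only interval does not reflect.

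The granules are being developed to minimise the food effect (Protocol 1.6 and 3.1.1), and Protocol 3.1.1 expects a smaller effect with low-fat local meals. SAP 19.1.2 frames these contrasts as bioequivalence, with two one-sided 5% tests. When a true ratio is near 1, a shift of several per cent could change how it is read.

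**Working it through.** **Inputs from the documents.** 12 participants per group (SAP 4.3); ln-scale models with treatment only (SAP 18.1.2, 19.1.2); two one-sided 5% tests, equivalent to a 90% interval. SAP 19.1.2 itself lists only point estimates and names no interval. The SAP gives no power, CV or equivalence limit, so there is no plan figure to reproduce.

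**Assumed inputs, not in the documents.** Exposure proportional to weight^(-b), with b = 0.75 to 1; SD of ln(weight), s_w, from 0.10 to 0.20; total CV of 30–60%.

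**1. Food effect: bias from a weight difference between the parts.** The ratio is multiplied by (W_ref/W_test)^b.

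| Mean weight, reference vs test | b = 0.75 | b = 1 |
|---|---|---|
| 65 vs 62 kg | 1.036 | 1.048 |
| 65 vs 60 kg | 1.062 | 1.083 |
| 70 vs 60 kg | 1.123 | 1.167 |

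If the fed group is the heavier one, the ratio is divided by these factors instead.

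**2. Coverage of the 90% interval.** Simulation with 12 versus 12 and 20,000 runs; CV 30% or 50%; (s_w, b) = (0.15, 0.75), (0.15, 1) or (0.20, 1).

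| Mean weight | Treatment-only: ratio factor, coverage | With ln(weight): ratio factor, coverage |
|---|---|---|
| Equal | 1.00, about 0.90 | 1.00, about 0.90 |
| 65 vs 60 kg | 1.06–1.08, 0.83–0.89 | about 1.00, about 0.90 |
| 70 vs 60 kg | 1.12–1.17, 0.65–0.84 | about 1.00, about 0.90 |

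The adjusted results are this clean because the simulated relation to weight is exactly log-linear and nothing else differs between the parts.

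**3. Part 1: chance imbalance only.** The SD of the difference in mean ln(weight) is s_w × sqrt(2/12). At s_w = 0.15 this is 0.061, so a 1-SD imbalance moves the ratio by exp(0.75 × 0.061) = 1.047 to exp(1 × 0.061) = 1.063. This is sampling error inside a valid interval. For comparison, the 90% interval is already about ×/÷1.23 at CV 30% and ×/÷1.39 at CV 50%.

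**4. Precision in Part 1.** The share of ln variance explained is R² = (b × s_w)²/ln(1 + CV²), about 2% to 46% over the assumed range. The corresponding change in interval width runs from about 2% wider to about 25% narrower. In the simulation the ln-scale half-width goes from 0.203 to 0.193 (CV 30%, s_w 0.15, b 0.75), but only from 0.327 to 0.326 at CV 50%.

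**5. Cost if weight has no effect and group mean weights differ only by chance.** Relative half-width, approximately:

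- Two groups of 12: sqrt(1 + 1/20) × t(0.95, 21)/t(0.95, 22) = 1.0247 × 1.7207/1.7171 = 1.027, break-even R² = 1 - 1/1.027² = about 5%.
- Groups 2–5 in one model (48 participants): sqrt(1 + 1/42) × t(0.95, 43)/t(0.95, 44) = 1.0118 × 1.6811/1.6802 = 1.012, break-even R² = about 2.4%.

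**6. Cost if the parts do differ in weight.** The adjusted interval can widen by more. With 70 vs 60 kg, CV 50%, s_w 0.15 and b 0.75, the two-group half-width goes from 0.327 to 0.370, while coverage rises from 0.84 to about 0.90. The extra width reflects uncertainty that the treatment-only interval omits.

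**The case against.** **Part 1 contains no error.** A reader might infer that leaving weight out undermines the primary ratio. It does not. Randomisation makes the unadjusted ratio unbiased, its 90% interval covers as it should, and Protocol 10.8 defines the primary result as a plain ratio of geometric means. SAP version 1.0 is dated 19 December 2023, the planned first participant in was July 2023, and the trial is open-label with Part 1 PK reviewed before Part 2. A new primary covariate in Part 1 could therefore follow sight of the data. This stands, and it is why the treatment-only model should remain primary there.

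**No weight difference is documented.** A reader might also infer that the parts differ systematically in weight. The documents do not support that: entry criteria, site and catchment area are the same, and no section reports or predicts a difference. The concern is an unprotected contrast, not a demonstrated bias.

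**The sizes rest on assumptions.** The documents give no weight SD, slope or total CV, and nothing on how piperaquine exposure depends on weight. One exponent for every AUC and Cmax is a simplification. This stands.

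**The consequences are modest.** This is an unpowered pilot (Protocol 10.1, 10.2), and 6–17% is small beside the roughly 3-fold tablet food effect that the protocol cites. That is fair for a large effect with the high-fat meal. It is less convincing near a ratio of 1, where the SAP nevertheless plans bioequivalence tests.

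**It may be handled elsewhere.** Weight is tabulated by group in the PK set, so an imbalance would be visible, and Protocol 10.7 refers PK detail to a PK analysis plan that was not available for this review. A table shows an imbalance without correcting the ratio, however, and choosing an adjustment after seeing it would be hard to defend. SAP 19.1.2 specifies the model itself, so the change belongs there.

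**Conclusion.** The point holds for the food effect. SAP 19.1.2 estimates a non-randomised contrast with treatment as the only term, although a plausible confounder is already measured in every participant. If the parts differed in mean weight by 65 versus 60 kg, the ratios would shift by 6–8%, and 70 versus 60 kg would shift them by 12–17%. Coverage of a nominal 90% interval would fall to 0.83–0.89 and 0.65–0.84 respectively in the scenarios examined. These sizes depend on the assumed exponents; the coverage figures also depend on the assumed weight SD and total CV.

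The issue matters most for the low-fat meal, where Protocol 3.1.1 expects a reduced effect. It would matter equally for milk if that effect is small, although the documents state no expectation for milk.

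For Part 1 the treatment-only model is valid, and weight is only a precision option whose gain may be near nil.

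**What to change.** 1. In SAP 19.1.2, add ln(Day -1 body weight) as a fixed covariate in the GLM for each ln-transformed exposure metric, and report the unadjusted ratios alongside. State whether Groups 2–5 are fitted in one model or pairwise.
2. In the text of 19.1.2 and the title or footnote of Table 14.2.1.4, label the food-effect ratios as non-randomised comparisons between study parts.
3. In SAP 18.1.2, keep the treatment-only model as primary and add the ln(weight) model only as a prespecified sensitivity analysis.
4. Record the change in SAP section 5, with its date relative to the availability of Part 1 and Part 2 PK data.

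The cost is a few lines of SAP text and code and one degree of freedom. If weight has no effect and mean weights are similar, the interval is about 1% wider (Groups 2–5 together) to 3% wider (two groups of 12). It widens further if the parts differ in weight.

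The adjustment does not remove other between-part differences, such as calendar period or sex mix, so the non-randomised label is needed even with the covariate.

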19.1.1 Variables and derivations

- AUC_{0-72h} : Area under for the plasma concentration curve from time zero to 72 hours
- AUC_{0-168h} : Area under the plasma concentration curve from time zero to 168 hours
- AUC_{0-t} : Area under the plasma concentration curve from time zero up to the last quantifiable concentration
- $AUC_{0-\infty}$: Area under the plasma concentration-time curve from time 0 extrapolated to infinite time.
- C_{max} : Maximal plasma concentration

Comparisons of the Interest are as follows:

- Group 3: High-fat meal with Group 2: PQP dispersible granule
- Group 4: Low-fat meal representative of African diet with Group 2: PQP dispersible granule
- Group 5: Whole milk 250 ml with Group 2: PQP dispersible granule

19.1.2 Analysis

Population: Table: PK

Listing: PK

Stratification: Table: By part and group

Listing: By part, group, participant, timepoint & parameter

Statistics: The relative bioavailability will be assessed for PQP using the ratio of the geometric means for $AUC_{(0-72)}$, $AUC_{(0-168)}$, $AUC_{(0-t)}$, $AUC_{(0-\infty)}$, and C_{max} as follows:

For Part 2 the comparisons will be as follow.

- Group 3: High-fat meal (Fed) [test] over the Group 2 PQP dispersible granule (fasting) [reference]
- Group 4: Low-fat meal representative of African diet (Fed) [test] over the Group 2 PQP dispersible granule (fasting) [reference]
- Group 5: Whole milk 250 ml (Fed) [test] over the Group 2 PQP dispersible granule (fasting) [reference]

To determine bioequivalence between PQP dispersible granule (320 mg) [test] and each of different type of meal, ln-transformed PK parameters ($AUC_{(0-72h)}$, $AUC_{(0-168)}$, $AUC_{(0-t)}$, $AUC_{(0-\infty)}$, and C_{max}) will be

analyzed using Type III sum of squares, with the fixed effect of Treatment using General Linear Model (PROC GLM) of SAS software.

Each analysis of variance will include calculation of least square mean (LSM). Two 1-sided tests procedure at 5% level of significance will be used to compare the geometric LSM values of PK parameters determined after administration of test (different type of meal) and reference products.

Point estimates of the ratio of geometric least squares means of dispersible granules formulation between fed [high-fat meal, low-fat African meal, and milk] will be calculated and reported for In-transformed PK parameters.

Total subject variability for the dispersible granules formulation between fed [high-fat meal, low-fat African meal, and milk] PK data will be calculated and reported.

Summary statistics (i.e., mean, median, SD, CV%, minimum, maximum, n, geometric mean, geometric SD, and geometric CV%) will be calculated for blood concentrations for each time point and group. The same will be done for the PK parameters which will be listed for each individual and summarized by group.

19.2 To further evaluate the PK of a single oral dose of PQP granule formulation in the fasted state and different fed states in healthy adult participants.**19.2.1 Variables and derivations**

The following pharmacokinetic parameters will be calculated for piperaquine:

- C_{\max} : Maximal plasma concentration
- T_{\max} : Time at which the maximum plasma concentration occurs
- $t_{1/2}$: Terminal elimination half-life
- $AUC_{0-\infty}$: Area under the plasma concentration-time curve from time 0 extrapolated to infinite time
- AUC_{0-t} : Area under the plasma concentration curve from time zero up to the last quantifiable concentration
- AUC_{0-24h} : Area under the plasma concentration curve from time zero to 24 hours
- AUC_{0-72h} : Area under the plasma concentration curve from time zero to 72 hours
- AUC_{0-168h} : Area under the plasma concentration curve from time zero to 168 hours
- $\%AUC_{\text{extrap}}$: Percentage of AUC that is due to extrapolation from t_{last} to infinity
- $C_{\text{L/F}}$: Apparent total plasma clearance
- $V_{\text{z/F}}$: Apparent volume of distribution during the terminal phase
- λ_z : Terminal rate constant

